6.2.3 Outliers

No rules for outlier detection are planned.

7. Statistical Methods

7.1 General Principles

All data processing, summarization and analyses will be performed using Covance's SAS Environment / Version 9.3 (or later) of the SAS® statistical software package.

The following principles will be applied to all TFLs unless otherwise stated:

Table 1: General Principles for the Presentation of Results

Principle	Value
Significant tests and confidence intervals	No significance tests will be conducted for the purpose of this analysis. For the primary efficacy endpoint, a 2-sided 90% confidence interval for the responder rate (%) at trough on Day 91 will be presented by treatment group for MAA868 arms only. For the secondary endpoint, a 2-sided 90% confidence interval for the responder rate (%) at trough on Day 31 and Day 61 will be presented by treatment group for MAA868 arms only.
Treatment group labels and order presented	MAA868 120 mg MAA868 180 mg MAA868 XXX mg (TBD for optional third cohort) Placebo (where applicable) All Subjects (where applicable)
Study phase labels and order presented	Study phase is not relevant to the analysis.
Visit labels and order presented	Listings will present data collected at all visits in the following order:

CONFIDENTIAL

Page 15 of 28

Statistical Analysis Plan

Sponsor Name: Anthos
Sponsor Protocol ID: ANT-004

Covance Study ID: 000000189471

Principle	Value
	
Screening (Visit 1)
 
Visits 2 - 10
 
TD Visit
 
EoS Visit
 
Unscheduled visits will be included in chronological order.
 
Tables will only present visits that correspond to the specified analysis.

Tables	
For endpoints related to inhibition of FXI the data will be tabulated for each trough visit by treatment group.
 
For endpoints related to the occurrence of major bleeding, cardiovascular, cerebrovascular, systemic arterial, and venous thromboembolic events, the data will be tabulated by treatment group.
 
For endpoints related to assessments performed at the study site visits, the data will be tabulated by each treatment group for all applicable scheduled visits.

Listings	
All data collected, as well as derived data used in the analyses, will be presented in listings by population/set, treatment group, and visit (where applicable), unless otherwise specified.

Descriptive summary statistics for continuous variables	
Non-PK parameters will be summarized by number of subjects (n), mean, standard deviation (SD), median, minimum (min), and maximum (max).
 
For a numeric result presented in the database with a "<", "≤", ">", or "≥" preceding the number, the value at the numeric part will be used in the summary.
 
PK Parameters will be summarized by number of subjects (n), mean, standard deviation (SD), median, minimum (min), maximum (max), and Geometric Mean.

Descriptive summary statistics for categorical variables	
Categorical variable will be summarized using frequency (N) and percentage (%).

Denominator for percentages	
Number of subjects in the analysis population/set, unless stated otherwise in table shell(s).

Display for percentages	
If the count is zero, then the percentage will not be presented. Otherwise, percentages will be rounded to 1 decimal place.

Include "Missing" as category	
Yes, when the number missing is greater than zero for at least one treatment group.

CONFIDENTIAL

Page 16 of 28

Statistical Analysis Plan

Sponsor Name: Anthos
Sponsor Protocol ID: ANT-004

Covance Study ID: 000000189471

Principle	Value
Display same number of decimal places as collected value	Minimum Maximum
Display to one more decimal place than collected value	Mean Standard Error Mean Difference Median Confidence Interval
Display to two more decimal places than collected value	Standard Deviation
Date Format	DDMMYYYY
Source footnotes	Each table will have a footnote that lists the source data listing(s). Each figure will have a footnote that list the source table(s).
Dictionary names and versions	The dictionary names and versions will be included in a footnote in all AE and prior or concomitant medication TFLs that present coded terms from the dictionaries.

7.2 Subject Disposition and Data Sets Analyzed

Subject disposition will be listed and summarized by treatment group and overall and will include the number and percentage of subjects:

- Screened
- Randomized
- Randomized and not treated
- Treated
- Included in each study set (Safety, FAS, PP, PK/PD).

In addition, the number and percentage of subjects who complete the study and who discontinue early, including a breakdown of the primary reasons for discontinuation, will be presented for all screened subjects.

A summary of the reasons for screen failure as well as the number of subjects screened but not randomized will be produced. No other information for screen failures will be presented.

CONFIDENTIAL

Page 17 of 28

Document Date: 18-MAR-2021

ST-AD-008 version 05

7.3 Protocol Deviations

Both important and non-important protocol deviations will be listed. Important protocol deviations defined in [section 5.4.1](#) will be excluded from PP set, and summarized by treatment group. The deviations will be identified before data are unblinded.

7.4 COVID-19 Impact

All COVID-19 related study disruptions will be listed for each subject by investigational site. Disruptions causing dosing schedule deviations and missing visits will be listed separately for each subject. COVID-19 related protocol deviations will be summarized by treatment for the FAS.

7.5 Demographics and Other Baseline Characteristics

Demographic and baseline characteristics will be listed and summarized by treatment group and overall for the randomized set and FAS. Standard descriptive statistics (see [Table 1](#)) will be presented for the continuous variables of:

- Age (years) [calculated as (informed consent date – date of birth)/365.25 and reported as whole years]
- Height (cm)
- Weight (kg)
- Body mass index (kg/m²)

Standard descriptive statistics (see [Table 1](#)) will be presented for the categorical variables of:

- Age group (years) (grouped by decades: 18-20, 21-30, ... 81-85)
- Gender
- Race
- Ethnicity

No formal tests of statistical significance will be performed on the demographic and baseline data. The mean of the three screening measurements for SBP and DBP will be used. A listing of subjects with abnormal physical examination findings at screening will be presented. Other baseline measurements will be summarized by treatment group with the post-baseline measurements.

7.5.1 Medical History

Medical history will be coded using the Medical Dictionary for Regulatory Activities (MedDRA) version 22.0. All medical history will be listed, and the number and percentage of subjects with any medical history will be summarized separately for the randomized set and FAS by system organ class (SOC) and preferred term (PT) for each treatment group and overall.

7.5.2 Previous and Concomitant Medications

Medications received prior to or concomitantly with study drug will be coded by Covance using the WHO Drug Version March 2019 Global Dictionary Version B3 Anatomical Therapeutic Chemical (ATC) Classification codes.

Prior medications and concomitant medications will be listed and summarized separately for per protocol set and FAS. The number and percentage of subjects using each medication will be displayed together with the number and percentage of subjects using at least one medication within each therapeutic class (ATC-Level 2), chemical subgroup (ATC-Level 4), and generic term.

7.6 Measurements of Compliance

Treatment compliance will not be summarized for this study.

Dose compliance will be calculated for each subject as: (number of doses occurring within protocol-defined study day window within 10% of the planned dose) / (number of doses received), then multiplied by 100.

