The study is comprised of 3 periods: screening period, treatment period, and follow-up period. The screening period may last up to 4 weeks. The treatment period is 91 days and consists of 3 monthly subcutaneous doses of MAA868 (or matching placebo). Study drug is administered at the study site on day 1 (visit 2), day 31 (visit 4), and day 61 (visit 6). During the treatment period, subjects will return to the study site on day 11, day 31, day 41, day 61, day 71, and day 91 for safety assessments. The follow-up period is 79 days and continues to day 170, allowing a 110-day washout period from the last study drug administration. During the follow-up period, subjects will return to the study site on day 101, day 121, and day 170 (EoS) for additional safety evaluations.

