5.4.1 Important Protocol Deviations Leading to Exclusion from the PP

Only those important protocol deviations considered to have a major effect on efficacy will lead to complete exclusion of the subject from the PP. For the purposes

Statistical Analysis Plan

Sponsor Name: Anthos
Sponsor Protocol ID: ANT-004

Covance Study ID: 000000189471

of this study, the list of subjects that have been identified as important protocol deviations leading to exclusion from the PP set is listed below. It is considered that the occurrences of any of these criteria might have an important influence on the primary efficacy endpoint.

Missed IMP dose

Missed FXI collection at V8, D91

Missed FXI collection at V2, Randomization

Out of window visit greater than 30 days

Most of the important protocol deviations leading to exclusion from the PP set require clinical or medical monitoring interpretation. These criteria will be reviewed prior to database lock. Important protocol deviations leading to exclusion from the PP set occurring during the study will be reviewed and approved by Anthos prior to database lock. Should additional important protocol deviations leading to exclusion from the PP set, not anticipated at the time of preparing this SAP, be identified during the study they will be documented in a SAP amendment and included in all relevant protocol deviation reviews and approvals.

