6.1 Time points and Visit Windows

Day 1 is defined as the day subjects receive the first dose of study drug. Relative days after Day 1 are calculated as (assessment date – Day 1 date) + 1. Relative days prior to Day 1 are calculated as (assessment date – Day 1 date). The day prior to Day 1 is Day -1.

Baseline is defined as the most recent result obtained prior to first administration of study medication. This occurs at visit 2 (day 1 pre-dose). If the assessment is not performed at visit 2, the value from visit 1 (screening) will be used. If this value is not present, there will be no baseline value.

Trough FXI levels will only be used if they are considered "on treatment". A measurement is considered "on treatment" if it is collected within 30 (± 5) days after the last administration of MAA868.

CONFIDENTIAL

Page 13 of 28

Statistical Analysis Plan

Sponsor Name: Anthos
Sponsor Protocol ID: ANT-004

Covance Study ID: 000000189471

All data will be analyzed using nominal study visits as defined in the schedule of assessments and eCRF. Unscheduled visits will be listed but not tabulated. No visit windows will be applied for summary and analysis.

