7.8.1 Extent of Exposure and Compliance

Study drug exposure will not be summarized for this study. Dose compliance will be summarized by treatment group and overall for the MAA868 arms only.

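### SAP 7.6 divides dose compliance by doses received, so missed doses cannot lower it, and no exposure summary fills the gap

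*SAP*

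**What the plan says.** SAP 7.6 gives a per-subject ratio. The numerator is the "number of doses occurring within protocol-defined study day window within 10% of the planned dose"; the denominator is the "number of doses received), then multiplied by 100". The same section opens with "Treatment compliance will not be summarized for this study" and does not define that term.

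SAP 7.8.1 states "Study drug exposure will not be summarized for this study" and then "Dose compliance will be summarized by treatment group and overall for the MAA868 arms only".

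The regimen is three injections, on Days 1, 31 and 61 (SAP 2.2). On timing, SAP 6.1 says "Day 1 is defined as the day subjects receive the first dose of study drug".

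Other sections do deal with missed doses:
- SAP 5.4.1 lists "Missed IMP dose" among the important deviations that exclude a subject from the per-protocol set.
- SAP 7.3 lists all deviations and summarizes those important ones by treatment group.
- SAP 7.2 counts subjects in each analysis set and gives reasons for early discontinuation.
- SAP 7.4 lists COVID-19 disruptions to dosing by subject and summarizes COVID-19 deviations by treatment.
- SAP 7.8.2 tabulates adverse events that led to stopping study drug.

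**The concern.** A compliance percentage is normally read as the share of the planned regimen that was delivered. This ratio cannot carry that meaning, because an omitted dose leaves both numerator and denominator. It describes the timing and amount of the doses that were given, and says nothing about doses that were not.

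This matters because Protocol 5.6 (Amendment 2) permits dosing interruptions for logistical reasons such as COVID-19 travel restrictions, and the Day 91 trough is meant to follow a third dose. With about 12 active subjects per cohort, one or two incomplete courses are relevant to how the results are read. A compliance table showing 100% would suggest that there were none. No exposure table corrects that impression, and the placebo arm has no compliance summary at all, although safety is to be judged against placebo.

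**Working it through.** **Inputs.** Planned doses: 3 (SAP 2.2). Numerator and denominator: SAP 7.6. The first dose defines Day 1 (SAP 6.1), so it is on time by construction and counts as correct if the amount is within 10% of plan. Active subjects per cohort: 12 (Protocol 5.3). The documents state no compliance figure to reproduce.

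**Formulas.** Let *c* be the doses given in window and in amount, and *r* the doses received.
- SAP 7.6: 100 × *c* / *r*
- Against plan: 100 × *c* / 3

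| Received (*r*) | Correct (*c*) | SAP 7.6 | Against plan |
|---|---|---|---|
| 1 | 1 | 1/1 = 100% | 1/3 = 33.3% |
| 2 | 2 | 2/2 = 100% | 2/3 = 66.7% |
| 2 | 1 | 1/2 = 50% | 1/3 = 33.3% |
| 3 | 2 | 2/3 = 66.7% | 2/3 = 66.7% |
| 3 | 3 | 3/3 = 100% | 3/3 = 100% |

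Where at least one dose was correct, the two columns agree only if all three doses were received. Under the SAP formula, a third dose given out of window costs a subject 33.3 points, while omitting that dose costs nothing.

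**Arm mean (illustration).** Assume that *k* of 12 subjects stop after one correct dose and the others are fully compliant. The mean against plan is (*k* × 33.3 + (12 − *k*) × 100) / 12.
- *k* = 0: 100%
- *k* = 1: (33.3 + 1100) / 12 = 94.4%
- *k* = 2: (66.7 + 1000) / 12 = 88.9%
- *k* = 3: (100 + 900) / 12 = 83.3%

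The SAP mean is 100% in all four cases. If instead 3 of 12 each miss one dose, the mean against plan is (9 × 100 + 3 × 66.7) / 12 = 91.7%, and the SAP mean is again 100%.

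**Restarts.** Protocol 5.6 lets a subject who had one dose before an interruption begin again with the first dose, so that subject can receive 1 + 3 = 4 doses. Dividing by 3 gives 4/3 = 133% if all four count as correct, which requires the windows to be re-anchored at the restart. If windows stay tied to the original Day 1, the restarted doses fall out of window and the result is 1/3 = 33.3%. A denominator of 3 therefore needs a counting rule.

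**Link to the primary analysis.** SAP 7.7.1 uses only values collected 30 (±5) days after the last dose. A subject who missed the Day 61 dose is about 91 − 31 = 60 days from the last dose at Day 91 and is left out of the responder denominator. A subject who missed only the Day 31 dose is 91 − 61 = 30 days out and stays in. The compliance ratio enters neither step.

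**The case against.** The strongest reply is that missed doses are reported elsewhere, and this stands. A reader might infer from the formula that they vanish from every summary. The documents do not support that: SAP 5.4.1 and 7.3 make a missed dose an important deviation summarized by treatment group, with no restriction to the MAA868 arms, and SAP 7.2 and 7.4 add analysis-set counts, discontinuations and COVID-19 reporting. Doses are given by study staff at the site, so an omission should come to light as a deviation. What these provisions do not specify is how many subjects received one, two or three doses, and they do not correct a compliance figure that stays at 100%.

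Two further objections also stand. The ratio is not a measure of timing alone, because its numerator also requires the amount to be within 10% of plan. And SAP 7.6 and 7.8.1 need not contradict each other: one declines to summarize *treatment* compliance, the other summarizes *dose* compliance. As treatment compliance is never defined, this is unclear terminology and not a proven conflict.

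Finally, the ratio is descriptive, and the documents do not use it for any endpoint, interval, analysis set or cohort decision. That limits the importance of the point but does not make the formula right.

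**Conclusion.** The denominator should be corrected. As written, a subject who received one third of the regimen can score 100% and rank above one who received all of it at 66.7%. In an arm of 12, up to three subjects stopping after the first dose would leave the reported mean at 100%, where the mean against plan would be as low as 83.3%. These arm means rest on assumed numbers of subjects stopping and assume that all other doses are correct; the subject-level figures follow directly from the formula.

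The effect is on the reported compliance figure and its interpretation. A reader might infer that the responder rate is also distorted, but the documents do not support that. The rate and its Clopper-Pearson interval are computed from on-treatment trough values and do not change with the compliance formula. A subject who missed only the Day 31 dose can still enter the Day 91 rate after two doses. That follows from the on-treatment rule, and a corrected mean compliance figure would not by itself identify such a subject.

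**What to change.** In the SAP:

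1. In 7.6, change the denominator to the number of planned doses (3) and keep the numerator's timing and amount conditions.
2. State how subjects who restart under Protocol 5.6 are counted: which doses enter the ratio and which Day 1 sets the windows. The SAP names protocol Version 2.0 as its source, and section 5.6 of that version has no restart provision, so the rule has to be added.
3. In 7.8.1, add a table of the number of doses received (1, 2 or 3) by arm, including placebo, on the safety set. Show any subject with a fourth dose according to the rule in step 2.
4. In 7.6, define treatment compliance and say how it differs from the dose compliance that 7.8.1 summarizes, or use one term throughout.

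The cost is a short text edit, one counting rule and one small table from dosing data already collected. Sample size and the efficacy analyses are unaffected.

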7.7 Efficacy

All efficacy analysis will be presented by treatment group for MAA868 arms only using the PK/PD set. No comparisons to the placebo or statistical tests will be conducted for efficacy endpoints.

7.7.1 Primary Efficacy Analysis

The primary analysis variable is a binary variable indicating whether a subject will achieve a certain percentage FXI inhibition at trough on Day 91. The response rate per treatment group will be calculated by number of subjects who achieve targeted FXI inhibition rate divided by the total number of subjects with an "on treatment" measurement in the treatment group. The dose regimens and targeted FXI inhibition achievement for Cohorts 1 and 2 are as follows:

CONFIDENTIAL

Page 19 of 28

Statistical Analysis Plan

Sponsor Name: Anthos

Sponsor Protocol ID: ANT-004

Covance Study ID: 000000189471

Cohort 1 (MAA868 120 mg monthly or placebo): Targeted to achieve $\geq 50\%$ FXI inhibition in 90% of subjects at trough (Day 91).

Cohort 2 (MAA868 180 mg monthly or placebo): Targeted to achieve $\geq 90\%$ FXI inhibition in 90% of subjects at trough (Day 91).

Cohort 3 (MAA868 TBD mg monthly or placebo): Targeted to achieve \geq TBD% FXI inhibition in 90% of subjects at trough (Day 91).

The "on treatment" trough FXI levels will be used for the primary analysis, where "on treatment" FXI level is defined as a value which is collected within 30 (± 5) days after the last administration of MAA868. The estimate of the responder rate (%) at Day 91 will be presented for each dose regimens of MAA868 together with 2-sided 90% confidence intervals computed via the Clopper-Pearson exact binomial method.

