8.3. General Considerations

All efficacy analysis will be based on the Full Analysis Set or Per Protocol Set and will be performed based on the assigned treatment arm at the randomization. Only descriptive statistics will be summarized, no statistical inference will be calculated in efficacy.

Safety analysis will be performed using Safety Set. Subjects will be analyzed based on the actual treatment taken.

PK and PD analysis will be based on PK/PD Analysis Set.

Continuous variables will be summarized by number of subjects [n], mean, standard deviation [SD], median, minimum [min], and maximum [max]. Categorical variable will be summarized using frequency [N] and percentage [%].

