8.5. Efficacy Analysis

Primary Efficacy Outcome Measures

Within each treatment cohort patients will be randomized 3:1 to active drug or placebo.

The primary analysis variable is whether a subject will achieve a certain percentage FXI inhibition at trough (Day 91). The response rate per treatment group will be calculated by number of subjects who achieve targeted FXI inhibition rate divided by the total number of subjects in the treatment group. The dose regimens and targeted FXI inhibition achievement for Cohorts 1 and 2 are as follows

Cohort 1 (MAA868 120 mg monthly or placebo): Targeted to achieve $\geq 50\%$ FXI inhibition in 90% of subjects at trough (Day 91).

Cohort 2 (MAA868 180 mg monthly or placebo): Targeted to achieve $\geq 90\%$ FXI inhibition in 90% of subjects at trough (Day 91).

The “on treatment” trough FXI levels will be used for the primary analysis, where “on treatment” FXI level is defined as a value which is collected within 30 (± 5) days after the last administration of MAA868. The estimate of the responder rate (%) at Day 91 will be presented for each dose regimens of MAA868 together with 2-sided 90% confidence intervals (CI) computed via the Clopper-Pearson exact binomial method.

Secondary Efficacy Outcome Measures

The secondary efficacy analysis is to evaluate the proportion of subjects achieving FXI inhibition $\geq 50\%$, $\geq 80\%$, and $\geq 90\%$ at trough after the first and second dose (Day 31 and Day 61) at 3 dose levels of MAA868. The analyses described for the primary endpoint will be repeated for the secondary efficacy variables as follows:

- Cohort 1 (MAA868 120 mg monthly or placebo): at Day 31 and 61.
- Cohort 2 (MAA868 180 mg monthly or placebo): at Day 31 and 61
- Cohort 3 (MAA868 TBD mg monthly or placebo): at Day 31 and 61

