4.2 Pharmacodynamic Variables

The following Pharmacodynamic (PD) parameters will be estimated:

- Free FXI
- Activated partial thromboplastin time (aPTT)
- Total FXI
- FXI coagulation activity (FXI:C)

CONFIDENTIAL

Page 11 of 28

PD parameters are used in the primary endpoint analysis. PD samples will be obtained and evaluated in all subjects at all dose levels. PD parameters aPTT, Free FXI, and Total FXI are collected at all visits. FXI coagulation activity is collected at day 1, day 61, day 91, and EoS. Concentrations of plasma total MAA868 (i.e., MAA868 that is bound to FXI or not bound to FXI) will be measured in plasma and determined by a validated LC-MS/MS method.

5. Analysis Populations/Sets

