5.5 PK/PD Analysis Set

The PK/PD analysis set will include all subjects who received at least one dose of study drug and have at least one PK/PD assessment.

6. Data Handling

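### SAP 7.7.1 takes subjects without an on-treatment Day 91 value out of the primary denominator, and SAP Section 8 declares neither this nor the related analysis-set changes

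*SAP*

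**What the plan says.** **Denominator.** Protocol 8.5 defines the response rate as the number of subjects who "achieve targeted FXI inhibition rate divided by the total number of subjects in the treatment group". Protocol Version 2.0, which the SAP names as its source, has the same wording. SAP 7.7.1 instead takes "subjects who achieve targeted FXI inhibition rate divided by the total number of subjects with an" on-treatment measurement. Both documents define on-treatment as 30 (±5) days after the last MAA868 dose, and the protocol itself says that on-treatment "trough FXI levels will be used for the primary analysis, where" that definition follows.

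**Analysis set.** Protocol 8.3 states: "All efficacy analysis will be based on the Full Analysis Set or Per Protocol Set", by assigned arm. It also states: "PK and PD analysis will be based on PK/PD Analysis Set", and protocol 8.2 analyses that set by actual treatment. Free FXI falls under both headings: protocol 7.5 lists it as an efficacy assessment, and SAP 4.2 says "PD parameters are used in the primary endpoint analysis". SAP 7.7 has all efficacy analysis "presented by treatment group for MAA868 arms only using the PK/PD set". SAP 5.5 defines that set as "all subjects who received at least one dose of study drug and have at least one PK/PD assessment". Neither section says whether assigned or actual treatment applies.

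**FAS.** Protocol 8.2 removes only subjects randomized in error who were not dosed. SAP 5.3 also requires a dose and a post-baseline assessment.

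**Backstops.** SAP 6.2.2 uses observed data without imputation, 7.7.3 plans no sensitivity analysis, and Section 8 reports no departure from the protocol.

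**Thresholds.** Protocol 2.1 and SAP 3.1 list ≥50%, ≥80% and ≥90% inhibition at Day 91. Protocol 8.5 and SAP 7.7.1 attach one target to each dose: ≥50% for 120 mg and ≥90% for 180 mg.

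**The concern.** The primary result is one proportion per active arm of about 12 subjects, presented beside a projection that 90% of subjects reach the target. In arms this small, one or two subjects moving in or out of the denominator shift the estimate by several points. Under the protocol's wording, a subject without a usable Day 91 trough stays in the denominator and cannot count as a responder. Under the SAP's wording, that subject disappears from the rate. A reader told that nothing changed would not know which rate they were looking at, and the plan produces no second rate to compare. The default in SAP Table 1, which takes percentages over the whole analysis set unless a table shell says otherwise, adds to the uncertainty.

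**Working it through.** **1. Reproduce the plan's figure.** SAP 2.3 gives an exact 90% interval of 0.661 to 0.996 for 11/12. The two-sided 90% Clopper-Pearson limits for x of n are: lower = 5% quantile of Beta(x, n−x+1); upper = 95% quantile of Beta(x+1, n−x). For x = 11 and n = 12 this gives 0.6613 to 0.9957, which matches. The illustration uses all 12 active subjects.

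**2. Direction.** Let N be all subjects in the arm, n those with an on-treatment value and r the responders. Then r/n − r/N = r(N−n)/(nN). This is zero if n = N or r = 0, and positive otherwise.

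**3. Who is left out.**
- Visits inside the protocol Table 9 windows: from Day 61±2 to Day 91±2 is 89−63 = 26 to 93−59 = 34 days. This lies within 25 to 35, so nobody is lost.
- Third dose missed, Day 91 sampled on schedule: from Day 31±2 is 89−33 = 56 to 93−29 = 64 days. This is outside the window, so the subject is lost.
- Day 91 sample missed, or taken outside 25 to 35 days after the last dose: lost.
- A dosing interruption in which dose and visit both move together: not lost.

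**4. Size.** The planned active arm is 12 (12:4 allocation, protocol 5.3). The documents give no missing rate, so the cases below are assumptions, each with one observed non-responder. Intervals are 90% Clopper-Pearson.

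| Lacking a value | SAP denominator | All subjects | Gap (points) |
|---|---|---|---|
| 0 | 11/12 = 91.7% (66.1–99.6) | 11/12 = 91.7% (66.1–99.6) | 0 |
| 1, not replaced | 10/11 = 90.9% (63.6–99.5) | 10/12 = 83.3% (56.2–97.0) | 7.6 |
| 2, not replaced | 9/10 = 90.0% (60.6–99.5) | 9/12 = 75.0% (47.3–92.8) | 15.0 |
| 1, replaced | 11/12 = 91.7% (66.1–99.6) | 11/13 = 84.6% (59.0–97.2) | 7.1 |
| 2, replaced | 11/12 = 91.7% (66.1–99.6) | 11/14 = 78.6% (53.4–93.9) | 13.1 |

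The replacement rows apply because protocol 5.3 lets the sponsor replace subjects. Every interval contains 90%.

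**5. Against the PP set.** SAP 5.4.1 lists a missed dose and a missed Day 91 FXI sample as PP exclusions, so for those subjects the gap between the SAP rate and a PP rate is 0. A Day 91 sample that is 6 to 30 days late falls 36 to 60 days after a Day 61 dose. It is not on-treatment, yet it is not past the listed 30-day exclusion. With one missed dose and one such late sample, the SAP rate is 9/10 = 90.0%, a PP rate is 9/11 = 81.8% (53.0–96.7), and the all-subject rate is 9/12 = 75.0%. This reads the 5.4.1 list literally; the SAP leaves most of these criteria to clinical review and allows additions by amendment.

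**The case against.** The protocol can be read the SAP's way. It already restricts the primary analysis to on-treatment troughs and has no rule for missing values, so counting missing as non-response is one reading among others. A travel-related missed dose, which protocol 5.6 permits, says nothing about pharmacodynamic response at trough. The analysis is descriptive, with no test and no decision rule tied to 90%. All of that stands, and it is why the on-treatment rate can remain primary. It does not make the two denominators the same, and it does not support the statement in Section 8.

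Three stronger readings are tempting, and the documents do not support them.

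- *The excluded subjects would be hidden.* SAP Table 1 adds a missing category whenever any arm has missing data, 7.3 lists deviations and summarizes the important ones by arm, and 7.4 lists COVID-19 disruptions. A missing row may already show the number left out. The table shells are not among the documents, so its absence cannot be claimed. What is not planned is the rate on the protocol's denominator.
- *Day 91 will be reported at one threshold per dose.* The per-dose wording is inherited from protocol 8.5 and describes modelled projections (protocol 3.3). SAP 2.1 and 3.1 name all three thresholds. SAP 7.7.2 repeats the primary analyses at all three, and Table 1 tabulates FXI inhibition at each trough visit by treatment group. Only a clarifying sentence is missing.
- *Moving to the PK/PD set breaches the protocol.* Protocol 8.3 points both ways for a measure that is both efficacy and PD. The SAP chose one of two ambiguous instructions without saying so. The set label should move few subjects, since the set needs only one dose and one PK/PD assessment and free FXI is sampled at every visit.

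**Conclusion.** The point holds as an undeclared change in the primary denominator, accompanied by an undeclared choice of analysis set and a narrower FAS definition. Section 8 of the SAP is incorrect as written. The effect is one-directional: the SAP rate exceeds the all-subject rate whenever at least one subject lacks an on-treatment Day 91 value and at least one responds. Under the assumed cases the gap is 7.1 to 7.6 points for one such subject and 13.1 to 15.0 for two, depending on whether they are replaced. It is zero if everyone has a value. Against a PP rate it can also be zero. A reader might infer that the change decides whether a dose meets its target. It can move the point estimate from 90.0% to 75.0%, but every interval computed contains 90% and no decision rule exists. Worth fixing before the results are tabulated. The finding is firm on the wording; its size rests on assumed missingness.

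**What to change.** All changes are to the SAP.

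1. Correct Section 8 to declare the on-treatment denominator, the use of the PK/PD set for efficacy, and the changed FAS definition. In 7.7, give the reason for the set and state whether assigned or actual treatment applies.
2. Keep the on-treatment rate as primary. Add one supportive rate by assigned arm on the FAS as protocol 8.2 defines it, including any subjects who were replaced, with no on-treatment Day 91 value counted as non-response. The FAS in SAP 5.3 would not restore the protocol's denominator. Beside the rate, show the number excluded from the on-treatment rate by reason: missed dose, missed sample, sample outside 30±5 days, withdrawal. The deviation summaries in 7.3 already supply much of this.
3. As a minor clarification, state in 7.7.1 that ≥50%, ≥80% and ≥90% at Day 91 are reported for every MAA868 dose arm with 90% Clopper-Pearson intervals.

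The cost is a SAP amendment and a few table rows. The supportive figure will look less favourable if values are missing, and it counts travel-related missed doses as non-response, so it should stay supportive. No protocol amendment is needed for this alone; protocol 8.5 can be aligned if the protocol is amended for another reason.
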